- b. During the intervention period, prescribers in participating hospitals still have access to paper-based prescribing guidelines distributed at the start of the study. Mobile phone prescribing guidelines surveys (Appendix A11) will be used as a tool to access the use of the mobile phone app prescribing guidelines and the paper prescribing guidelines at the end of the study

Figure 2: Study procedures of SW-CRT on Evaluation of Lao-language antimicrobial use guidelines mobile app

	Study phase				
	Pre-study phase				
Hospital 6	PPS+Report	PPS+Report+Paper-based	PPS+Report+Paper-based	PPS+Report+Paper-based	PPS+Report+App+AMS
Hospital 5	PPS+Report	PPS+Report+Paper-based	PPS+Report+Paper-based	PPS+Report+Paper-based	PPS+Report+App+AMS
Hospital 4	PPS+Report	PPS+Report+Paper-based	PPS+Report+Paper-based	PPS+Report+App+AMS	PPS+Report+App+AMS
Hospital 3	PPS+Report	PPS+Report+Paper-based	PPS+Report+Paper-based	PPS+Report+App+AMS	PPS+Report+App+AMS
Hospital 2	PPS+Report	PPS+Report+Paper-based	PPS+Report+App+AMS	PPS+Report+App+AMS	PPS+Report+App+AMS
Hospital 1	PPS+Report	PPS+Report+Paper-based	PPS+Report+App+AMS	PPS+Report+App+AMS	PPS+Report+App+AMS
	Month 0	Month 4	Month 8	Month 12	Month 16
	Activity at month 0	Activity at month 4	Activity at month 8	Activity at month 12	Activity at month 16
	AMS survey for all sites	AMS survey*	AMS survey*	AMS survey*	AMS survey for all sites
	Pre-prescribing survey	AMS training*	AMS training*	AMS training*	Prescriber feedback survey on the App guideline**
	Introduce paper-based guideline	Introduce App guideline*	Introduce App guideline*	Introduce App guideline*	
		Prescriber feedback survey on paper-based guideline*	Prescriber feedback survey on paper-based guideline*	Prescriber feedback survey on paper-based guideline*	
			Prescriber feedback survey on the App guideline**	Prescriber feedback survey on the App guideline**	

* This activity will only be performed in a new selected paired hospital

** This activity will only be performed 4 months after introducing App guideline in each paired hospital

c.4 Contamination prevention

Although the clusters are geographically quite remote from each other, travel and communications between doctors in Laos is quite frequent. There is a possibility of contamination of the app to the reference group (however this is judged to be unlikely). The research team will record this if it occurs. Examples of how this could happen are:

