3.6 Endpoints

Primary endpoint

The proportion of antimicrobial prescriptions adherent with prescribing guidelines delivered by mobile phone app versus paper-based prescribing guidelines at month 16 (12 months' exposure in each group)

Secondary endpoints

1. Total antimicrobial defined daily doses (DDDs) prescribed in mobile phone app versus paper-based groups of 12 months' exposure in each group

2. Proportion of patients prescribed antimicrobials by the intravenous route in mobile phone app versus paper-based groups of 12 months' exposure in each group
3. AMS knowledge level of prescribers prescribed in mobile phone app versus paper-based groups of 12 months' exposure in each group
4. Prescriber satisfaction/acceptability of the prescribing guidelines in mobile phone app versus paper-based groups of 4 months' exposure in each group
5. Total costs of antimicrobial prescribed in mobile phone app versus paper-based groups of 12 months' exposure in each group
6. Proportion of patients admitted to hospital receiving an antimicrobial prescription before and after introduction of the paper-based prescribing guidelines; and the mobile phone app prescribing guidelines + AMS training of 12 months' exposure in each group

Definitions of adherence to the guidelines

1. Full adherence with the guidelines = using correct antimicrobial agent (s) and correct dose based on the provided antimicrobial prescribing guidelines
2. Partial adherence with the guidelines = using correct antimicrobial agent (s) with incorrect dose based on provided antimicrobial prescribing guidelines
3. Non-adherence with the guidelines = using a different antimicrobial agent (s) compared to that suggested in provided antimicrobial prescribing guidelines

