There are different systems of OPD data recording in each hospital. This project will not create a new system for the hospital but follow the existing routine systems of each hospital, ensuring that we can capture all antimicrobial prescription data and the denominators. Scanned prescription files will be securely kept and discarded one month after the scanned date.

For more details of outpatient PPS data collection form, see **Appendix A3**. Outpatient PPS Form.

Point prevalence survey report

PPS reports of IPD and OPD survey will be available within one month after each survey. With the agreement of MoH, these PPS will support antimicrobial use surveillance in the country. The reports will be in the format of computer dashboard (AMU-Laos App) which will be published on the MoH website. Access to AMU-Laos App will be publicly available. Everybody can view the results of the survey but not access the raw data. AMU-Lao App will be managed and operated by the PI and a dashboard programmer only. AMU-Laos App will display prevalence of antimicrobial prescriptions of each time points in different participating hospitals, as well as the overview of antimicrobial prescriptions (e.g. classes, agents, route and indications) and pattern of the prescription by age, by specialty in both IPD and OPD. Paper reports will be also available via this AMU-Laos App (Appendix A4. *Point Prevalence Survey (PPS) of hospital antimicrobial use report format*). However, paper reports will be also provided by the research team to the participating wards/doctors as there is limited access to computers and internet in some areas of Laos.

a.3 Antimicrobial stewardship (AMS) knowledge survey

This survey will be performed before introduction of the paper version of the therapeutic and prophylactic antimicrobial prescribing guidelines (at month 0) and every 4 months before the implementation of the mobile phone app guidelines and AMS training in the paired hospitals starting the intervention. The survey will be performed again in month 16 in all study hospitals before the study ends. Therefore, each hospital will participate this AMS knowledge survey 3 times during the whole study period (1st time= at the start of the project, 2nd time= before entering to the intervention period and 3rd time= at the end of the project)

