This survey questionnaires will be in Lao language. The survey will provide information on the level of knowledge of rational antibiotic prescribing of prescribers before and after having access to paper prescribing guidelines and the app prescribing guidelines at different time points. For more details on what questions will be asked, see Appendix A5. *Antibiotic stewardship knowledge survey*.

Each survey will include 8 questions in total. The 8 questions will be randomly selected (simple random sampling – using a computer-generated random allocation sequence) from a set of questions in Appendix A5. The answers to all questions are in the guidelines.

Maximum 10 minutes will be requested to complete 8 questionnaires. The questionnaires will be multiple answers. There is no need to put the name of responders to the survey form but age, graduated year, department and speciality are needed. The survey will be conducted in the same day as introduction to the guidelines (paper (month 0)/app), introductory session of the guidelines (paper (month 0)/app), pre-prescribing guidelines survey (month 0), AMS training (only for those firstly enter to intervention period). Complete survey forms will be collected by the research team before starting the introductory session of the guidelines (paper (month 0)/app).

Pre-prescribing guidelines survey

The aim of conducting a pre-prescribing guidelines survey is to understand how prescribers prescribe antimicrobials and how much they use any prescribing guidelines in their routine work. This will provide some explanation as to what prescribers think about the provided prescribing guidelines. The survey will be performed once at the beginning of the study (month 0) after the first round of PPS and before introduction of the paper prescribing guidelines. Survey form (Appendix A9. *Pre-prescribing guidelines survey*) will be distributed to all prescribers at each study hospital and collecting back by the research team in the same day. The survey form contains 6 questions and it will take 5 minutes maximum to complete the survey.

Prescriber feedback survey on paper-based prescribing guidelines

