Guidelines have been developed based on existing national treatment guidelines, current data on infectious diseases, antimicrobial susceptibility patterns in Laos, as well as international recommendations. Availability of antimicrobials in Laos is also considered. The guidelines will be transformed to a mobile phone App which will make it easier for the clinicians to access. This would be more likely to benefit than harm patients or clinicians. However, this App and paper prescribing guidelines will be introduced to 6 general hospitals across Laos for 16 months before the prescribing guidelines mobile phone App will be adapted and distributed nationwide. There might be some risk that MoH would like to introduce the guidelines and the App before the study finishes if the results are very positive. In addition, it could be challenging to manage and control the travel of Lao doctors from one hospital to another as many trainings, workshops or conferences (not related to this project) are conducted across the country throughout the whole year. In addition, some doctors may have to leave their local hospital for further education. Apart from this project, another 18-month AMR program (supported by the Fleming fund) is also conducted in three participating hospitals (SV, XK and LNT) to improve the quality of infectious diagnosis in these three hospitals. This program plans to start at the same time as this project. This AMR program could have

some positive effect on antimicrobial stewardship knowledge of Lao doctors. In this case, the number of trainings and training materials (if applicable) provided by this AMR program will be recorded by our study team. There are also another three participating hospitals (MS, SVK and VTP) not included in the Fleming Fund project, this could allow us to compare MS knowledge level between hospitals with and without another AMR program in the analyzing stage.

Patient and doctor confidentiality

There will not be any record of patients' personal details to be able to identify any individual. Only patients' age, gender, weight and some information on antimicrobial prescription will be collected from hospital charts. There will not be any direct interaction between the research team and patients.

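### Endpoint 3 is worded as app versus paper, but the AMS knowledge survey never tests app and paper hospitals in the same month

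*Combined protocol and SAP*

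**What the plan says.** Section 3.6 defines secondary endpoint 3 as "AMS knowledge level of prescribers prescribed in mobile phone app versus paper-based groups of 12 months' exposure in each group". The synopsis words it almost identically. Objective 3, in the synopsis and in Section II, is different: it asks for a comparison before and after the app and the training.

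The survey schedule is in Section 3.7 a.3:

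- First survey, all hospitals: "This survey will be performed before introduction of the paper version of the therapeutic and prophylactic antimicrobial prescribing guidelines (at month 0".
- Second survey: "every 4 months before the implementation of the mobile phone app guidelines and AMS training in the paired hospitals starting the intervention". Figure 2 marks the month 4, 8 and 12 survey with the footnote "This activity will only be performed in a new selected paired hospital".
- Third survey: "The survey will be performed again in month 16 in all study hospitals before the study ends".

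The total is given as "each hospital will participate this AMS knowledge survey 3 times during the whole study period", and Appendix A12 repeats the same three occasions. On timing within the day, "Complete survey forms will be collected by the research team before starting the introductory session of the guidelines", so the second survey records knowledge while the hospital is still on paper.

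The Statistical analysis section compares the overall proportion of correct answers at three stages: baseline, after paper, and after app plus training. It says that outside AMR training, education and specialty will be considered. It names no adjustment for calendar time in this comparison.

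**The concern.** A stepped-wedge trial separates the intervention from time by observing, in the same period, some clusters that have switched and some that have not. For the knowledge outcome the survey schedule discards that feature. Hospitals that have switched are not tested again until month 16, when no hospital is left on paper alone. The randomised order of the pairs therefore gives endpoint 3 no concurrent comparison, although its wording promises one.

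At stake is attribution. If knowledge rises everywhere during the trial, or if scores rise because doctors sit the test again, the rise appears as a benefit of the app and training. The Risks section names one possible source: a separate 18-month AMR programme in Salavan, Xiengkhuang and Luang Namtha, planned to start with the trial, which the protocol accepts might improve doctors' stewardship knowledge.

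**Working it through.** **1. Rebuild the schedule.** Inputs: three surveys per hospital (Section 3.7 a.3), switches at months 4, 8 and 12 with one pair each (Section 3.5), and forms collected before the app session (Section 3.7 a.3).

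| Month | Neither guideline | Paper | App + training |
|---|---|---|---|
| 0 | 6 | 0 | 0 |
| 4 | 0 | 2 | 0 |
| 8 | 0 | 2 | 0 |
| 12 | 0 | 2 | 0 |
| 16 | 0 | 0 | 6 |

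The total is 6 + 2 + 2 + 2 + 6 = 18 hospital-surveys. 18 / 6 = 3 per hospital, which reproduces the protocol's figure.

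**2. Can the app effect be estimated?** Take 6 hospital columns, 4 month columns (4, 8, 12, 16) and 1 app column, which makes 11. The app column equals the month-16 column in all 18 rows. The rank is 10 with the app column and 10 without it, so the app effect is not estimable apart from month 16.

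**3. Alternative reading of the second survey.** If the four-monthly survey were meant for every hospital still on paper, there would be 24 hospital-surveys. No app hospital would be tested before month 16, and the rank would still be 10 of 11.

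**4. With an assumed trend shape.** Replace the 4 month columns by a linear month term and a post-paper term: 6 + 2 + 1 = 9 columns, rank 9. The effect can then be estimated, but only because the trend is taken to be straight.

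**5. Size under the planned comparison.** Mean paper survey month = (2×4 + 2×8 + 2×12) / 6 = 8. Mean app survey month = 16. The gap is 8 months, or two 4-month intervals. False effect = 2 × shared gain per 4 months. The plan gives no trend, so these are assumed values:

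| Gain per 4 months (points) | False app effect (points) |
|---|---|
| 0.5 | 1 |
| 1 | 2 |
| 2 | 4 |
| 3 | 6 |

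For retesting, every app survey is a third sitting and every paper survey a second. A practice gain of 1 point per sitting therefore adds 3 − 2 = 1 point.

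**6. With six added surveys** (first pair at month 8; first and second pairs at month 12). Month 8 then has 2 paper and 2 app hospitals, and month 12 has 2 paper and 4 app. There are 24 rows and the rank is 11 of 11. Feeding known patterns into this model (least squares, hospital-surveys weighted equally) gives the following app coefficients when the true effect is zero:

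- Shared trend of any shape: 0.
- Practice gain of 1 point per sitting: about 0.56, against 1 under the planned schedule.
- Trend of 1 point per 4 months only in the three AMR-programme hospitals: between −0.48 and +0.48, depending on the order of the pairs. Under the planned schedule the same trend gives between (2 + 1 + 1) / 6 = 0.67 and (3 + 3 + 2) / 6 = 1.33, where each term is a programme hospital's paper-to-app gap in 4-month intervals.

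**The case against.** The strongest reply is that this outcome is mostly presented as before-after already. Objective 3 says so, and the analysis compares stages in sequence; only the endpoint line claims an app-versus-paper contrast. That stands. It narrows the problem to a mismatch between endpoint 3 and the rest of the plan, plus a missing caveat on attribution.

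One might infer that no model could rescue the contrast. That is too strong: because the paper surveys are staggered, a linear trend is separable. But the plan specifies no such model, and its credibility would rest on the assumed shape.

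One might also infer that the documents predict knowledge gains from several directions. They do so for the AMR programme only. The Ministry training in the Introduction is for unnamed pilot hospitals, and nothing says that the PPS reports raise knowledge scores. For the AMR programme, the protocol will record the training given, take outside training into account, and compare hospitals with and without the programme. These are real safeguards, but they do not deal with trends common to all six hospitals or with retesting.

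Familiarity is lessened because each survey draws 8 questions at random from the 18 in Appendix A5. It is not removed: two independent draws share on average 8 × 8 / 18 = 3.6 questions.

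**Conclusion.** The point holds for endpoint 3 as worded. Paper and app hospitals are never tested in the same month, and with unrestricted month effects the app effect is not estimable. The planned comparison counts a shared background gain as app effect at 2 points for every 1 point per 4 months. The schedule and the multiplier come from the documents; the size of any trend is an assumption, and the documents do not show that one will occur.

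The point does not reach objective 3, which the schedule can serve as a before-after comparison. A reader might extend it to the primary endpoint, but the documents do not support that: the PPS runs in all six hospitals at every round, so months 8 and 12 contain both conditions. For a secondary endpoint with an inexpensive remedy, this is something the sponsor should change.

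**What to change.** Give form A5 also at month 8 in the first pair and at month 12 in the first and second pairs. Analyse with hospital and survey-month effects. As a sensitivity analysis, add a term for AMR-programme hospitals over time. That term is separable because the southern pair has one programme hospital (Salavan) and one without (Savannakhet), which switch together.

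**Cost.** Six more hospital-surveys (18 to 24) of at most 10 minutes per doctor, during the four-monthly PPS visits that already take place. Three downsides should be stated:

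- Doctors at hospitals that have already switched must be gathered for the form with no training session that day, while the PPS itself works from charts and prescription sheets.
- Figure 2 shows an app feedback form at months 8 and 12, but note a in Section 3.5 c.3 and the survey description in Section 3.7 place that form at month 16 only. It cannot be relied on as an existing contact until those texts are reconciled.
- Repeat sittings stay partly aligned with app status. Shared time trends are removed, but practice effects are only reduced, and a trend confined to the programme hospitals is not fully removed by the month effects alone.

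**If the surveys are not added,** reword endpoint 3 to match objective 3 as an uncontrolled before-after change. State that the change cannot be attributed to the app or training separately from calendar time. This costs nothing.

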measured cross-sectionally at month 0, 4, 8, 12 until month 16 after introduction of prescribing guidelines by mobile phone application versus paper-based (30). The model will compare all wedges in the intervention from month 4 to month 16 with all wedges in the reference arm from month 0 to month 12. The duration of exposure of each hospital to the reference or intervention arm will be included in the model as interaction term with the study arm in order to assess whether the duration of exposure is the effect modifier. The model will consider the correlation among the outcome's measurements from the same hospital (cluster) by adjusting for clustering in the model. Odds ratios and the corresponding confidence intervals will be obtained and reported. Tests of significance will be performed at 5% level. Analyses will be done using Stata 15.0 or higher. Likert scale analysis will be used to evaluate prescriber satisfaction with/ acceptability of paper-based compared to mobile phone app delivered antimicrobial prescribing guidelines. The satisfaction/acceptability scale will be assigned in six categories, including strongly agree=5, agree=4, neutral=3, disagree=2 and strongly disagree=1, no opinion/not use=0. Mann-Whitney test will be used to assess the differences between paper-based population and mobile phone app population. AMS knowledge level of prescribers will be assessed using questionnaires based on information in the prescribing guidelines. The overall proportion of correct answers in each time point will be compared (baseline, after paper-based guidelines (before AMS training and introduction of mobile phone app guidelines) and after AMS training and introduction of mobile phone app guidelines). Other factors such as extra AMR training program from hospital/MoH/other organizations, level of education and specialties of prescribers will also be taken into account.

Cost of antibiotic therapy will be calculated from the start date of treatment to the survey day. The unit costs for the antibiotics will be obtained from the [International Medical Product Price Guide](#).

Antibiotic defined daily dose (DDD) will be calculated using data (antibiotic agent, start date, dose and DDD of each antibiotic from www.whooc.no) from PPS in both IPD and OPD. Antimicrobial cost data from participating hospitals will also be collected each hospital pharmacy for comparison with international cost.

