Overall proportion of patients receiving an antimicrobial prescription by antimicrobial class at [name of hospital] from [survey start date] to [survey stop date]

[figure not shown]
Overall proportion of antimicrobial prescriptions in outpatient ward

[figure not shown]
Overall proportion of antimicrobial prescriptions in in-patient ward

Overall antimicrobial prescription by antimicrobial class and age at [name of hospital] from [survey start date] to [survey stop date]

In- patients [not real data - example chart only]

[figure not shown]

Proportion of antimicrobial prescriptions in children aged ≤ 15years

[figure not shown]

Proportion of antimicrobial prescriptions in adult aged > 15years

Outpatients [not real data - example chart only]

Overall antimicrobial prescription by 5 most common involved organs or systems

List of antimicrobial prescriptions at [name of hospital] from [survey start date] to [survey stop date]

Antimicrobial classes	Antimicrobial agent	Number of in-patient prescription (%); n= [total number of prescriptions]	Number of OPD prescription (%); n= [total number of prescriptions]
Beta lactams	Cephalosporins		
	[agent list]		
	Penicillin		
	[agent list]		
	Carbapenem		
	[agent list]		
Beta-lactam inhibitors			
	[agent list]		
Aminoglycosides	[agent list]		
Quinolones	[agent list]		
Macrolides	[agent list]		
Sulfonamides	[agent list]		
Nitroimidazoles	[agent list]		
Tetracycline	[agent list]		
Antiviral	[agent list]		
Antifungals	[agent list]		
Anti-TB	[agent list]		
Antimalarial	[agent list]		
Anti-helminthic	[agent list]		

A5. Antimicrobial stewardship (AMS) Knowledge survey

Antibiotic stewardship (AMS) knowledge survey

(Multiple answers are possible. Please circle your answers)

Date: ___/___/____, Graduation year from medical school: _____ Speciality: _____

Department: _____, Hospital: _____

1. Facts of antimicrobial resistance (AMR):

- a. Overuse or misuse of antimicrobials is accelerating the process of AMR
- b. AMR can occur naturally
- c. AMR can spread between people, animals and environment
- d. Poor infection control encourages the spread of AMR

2. Misuse or overuse of antibiotics include:

- a. Prescribing an oral narrow spectrum antibiotic (e.g. amoxicillin) to treat the common cold
- b. Always using broad spectrum antibiotics as first choice
- c. Completing an antibiotic treatment course even though the patient is feeling better

3. Which of the following is/are NOT correct?

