- d. Until discharge from hospital

13. Good practice for clean wound/surgery procedures regarding antibiotic prophylaxis is:

- a. No antibiotic prophylaxis is needed
- b. A single dose of IV combined antibiotic prophylaxis (e.g. ceftriaxone + metronidazole) is needed
- c. IV mono-antibiotic prophylaxis for a maximum of 3 days is enough
- d. A maximum of 5 days of oral antibiotic prophylaxis is needed

14. Which phrases are correct relating to viral respiratory infection:

- a. Antibiotics should be given to prevent bacterial complications in seasonal flu patients
- b. Antibiotics have no effect on colds
- c. Empirical treatment of bacterial co-infection of seasonal flu, should be for highly suspected cases only

15. A 3-year-old girl comes to you complaining of 4 days of fever, running nose, sneezing, sore throat, cough with normal vital signs, which antibiotic you recommend?

- a. Amoxicillin
- b. Penicillin

- c. Single dose of ceftriaxone
- d. No antibiotic is needed

16. Which statements are correct relating to the use of gentamicin?

- a. Gentamicin can cause serious nephrotoxicity and ototoxicity
- b. Gentamicin is often used for serious Gram-negative bacterial infections
- c. Gentamicin is cleared by the kidney, it is important to assess renal function before starting and during treatment courses
- d. Creatinine clearance should be monitored if drug level monitoring is not available

17. Which of the following is NOT effective in preventing the emergence or spread of antimicrobial resistant organisms?

- a. Good hand hygiene
- b. Treating infections for a longer period to prevent resistance
- c. Avoiding the use of antibiotics for treatment of colds and flu
- d. Vaccination

18. A 35-year-old man comes to you complaining of 2 days watery stool (~4-5 times a day), no history of fever, which antibiotic will you recommend?

- a. Ciprofloxacin
- b. Co-trimoxazole
- c. Azithromycin
- d. No antibiotic is needed, oral rehydration only

A6. Introductory session of therapeutic and prophylactic antimicrobial prescribing guidelines

The propose of the session is to introduce paper versions of therapeutic and prophylactic antimicrobial prescribing guidelines in both adult and paediatric version to all doctors in study hospitals. This session will not cover how to diagnose infectious diseases or prescribe antimicrobials.

Trainees: this session will be given to all hospital doctors in all study participant hospitals at the start of the study (month 0).

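### The AMS knowledge comparison makes no allowance for which 8 of the 18 questions were asked, and the plan does not say at what level the questions are drawn.

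*Combined protocol and SAP*

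**What the plan says.** Section 3.7, part a.3 (AMS knowledge survey), states: "Each survey will include 8 questions in total". It continues: "The 8 questions will be randomly selected", by computer-generated simple random sampling from the questions in Appendix A5. Appendix A5 numbers its questions 1 to 18; its heading reads "Multiple answers are possible. Please circle your answers". Part a.3 adds that "each hospital will participate this AMS knowledge survey 3 times during the whole study period": at month 0, just before the hospital crosses to the intervention (month 4, 8 or 12), and at month 16. Forms carry no name.

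The Statistical analysis section states: "The overall proportion of correct answers in each time point will be compared". The three conditions are baseline, after the paper guidelines, and after training plus the app. Extra AMR training is also to be considered, and "level of education and specialties of prescribers will also be taken into account".

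The plan mentions no common or anchor questions, no balancing by difficulty, no question effect, no scoring rule for partly correct answers and no named test for this endpoint. It does not say at what level the 8 questions are drawn.

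**The concern.** If everyone surveyed at one time answers one set of 8 and a later survey uses a fresh set, the two percentages differ for two reasons: what the doctors know, and how hard the questions are. The planned comparison cannot separate them. Recruiting more doctors does not help, because the difficulty of the set is common to all of them.

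The Appendix A5 questions are unlikely to be equally hard. They have three or four options, some ask what is not correct (questions 3 and 17), and some are short cases (15 and 18). They also differ in how close they lie to the training. Appendix A12 lists the switch from intravenous to oral treatment and penicillin allergy as training topics. Questions 7, 8, 10 and 11 address these directly, and a draw of 8 may contain anything from none to all four.

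At stake is secondary endpoint 3: a rise or fall in knowledge could be reported when none occurred. The primary endpoint is not affected.

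**Working it through.** The plan gives no sample size or error rate for this endpoint, so there is no figure to reproduce.

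**Inputs from the documents.** 18 questions in the bank, 8 per survey, three surveys per hospital, tests at 5% (taken as two-sided). Physicians by hospital (section 3.2): 222, 30, 66, 18, 60 and 30, total 426. By pair: north 66 + 18 = 84, centre 222 + 30 = 252, south 60 + 30 = 90.

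**Assumptions, not in the documents.** S, the SD across the 18 questions of the true proportion correct: 0.10, 0.15 or 0.20. Mean correct 60%. All physicians respond. Separate draws are independent.

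**Overlap of two draws.** Expected shared questions = 8 × 8/18 = 3.6. There are 43,758 possible sets, and two draws share at most 4 questions in 82% of cases.

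**Error of one draw.** SD of the mean difficulty of 8 questions from 18 = S × √[(1 − 8/18)/8] = S × √0.0694 = 0.264 S.

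**(a) One set per round, baseline versus month 16.** SD of the difference = 0.264 S × √2 = 0.373 S; 95% range = ±1.96 × 0.373 S = ±0.730 S.

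**(b) One set per round, baseline versus after paper.** The after-paper survey falls at month 4, 8 or 12, so it pools three draws. Weights 84/426, 252/426 and 90/426 have squares summing to 0.433. SD = 0.264 S × √(1 + 0.433) = 0.316 S; range ±0.618 S. After paper versus month 16 gives the same result, since it also sets three draws against one.

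**(c) One set per hospital and round.** The squared weights of the six hospitals sum to 0.327. SD = 0.264 S × √(2 × 0.327) = 0.213 S; range ±0.418 S.

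| Range with no change in knowledge (points) | S = 0.10 | S = 0.15 | S = 0.20 |
|---|---|---|---|
| (a) | ±7.3 | ±11.0 | ±14.6 |
| (b) | ±6.2 | ±9.3 | ±12.4 |
| (c) | ±4.2 | ±6.3 | ±8.4 |

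With equal hospital weights, (c) falls to ±3.0, ±4.5 and ±6.0.

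**(d) Separate draw per respondent.** The extra SD per doctor is 0.264 S, or 2.6 to 5.3 points. Ordinary sampling error on 8 answers at 60% correct is about √(0.6 × 0.4/8) = 17 points. With 84 doctors in each round the draw contributes ±1.96 × 2.6 × √(2/84) = ±0.8 points, up to ±1.6 for S = 0.20.

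**(e) One set reused throughout.** The difficulty term cancels.

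**False-positive rate.** This was simulated for a two-sided two-proportion test between two rounds with no true change (4,000 runs; 1,000 for per-respondent draws).

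| Design | Doctors per round | S = 0.10 | S = 0.15 | S = 0.20 |
|---|---|---|---|---|
| New set each round | 84 | 26% | 39% | 52% |
| New set each round | 426 | 56% | 67% | 76% |
| Same set, or one draw per respondent | 84 or 426 | 3–5% | 3–5% | 3–5% |

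The simulation treats answers as independent and ignores clustering by hospital and doctor. The test is an illustration, since the plan names none.

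**The case against.** The strongest reply is that the plan never says that each round gets a new set. The draw might be made once for the trial, in which case the problem does not arise, or separately for each doctor, in which case the comparison is unbiased and the added noise is small. This stands: a reader might infer that question set and round are certainly confounded, and the text does not go that far. But one set per survey is the most natural reading of the wording, and whether the endpoint can be interpreted should not depend on an unstated choice.

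A second reply is that random selection protects the comparison. It does so on average: the expected difference in difficulty is zero. A reader might infer a bias towards the app, and nothing in the documents supports that. The trial, however, realises only a few draws, and a test that ignores their variation has the wrong error rate.

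Third, the largest range describes only one comparison under one reading. That also stands. Pooling three draws narrows it, and a draw per hospital, which is possible because activities run hospital by hospital, narrows it further.

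Finally, the comparison is not wholly unadjusted: the list of prescriber factors is open-ended. None of those named corrects for which questions were asked.

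**Conclusion.** The concern holds in a limited form. As written, the plan allows, and most naturally implies, a comparison in which question difficulty is mixed with change in knowledge and left out of the test. The result is an error that averages zero and favours neither arm, with tests that are too liberal.

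Its size depends on the level of the draw and on an assumed spread of difficulty. For an item SD of 0.10 to 0.20, it runs from about ±7 to ±15 points at its largest (one set per round, baseline versus month 16) down to about ±4 to ±8 with a draw per hospital. It is small with a draw per respondent and absent with one reused set. The false-positive rates illustrate the one-set-per-round case only. The change is worth making because it is cheap, but it bears on one secondary endpoint.

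**What to change.** State the level of the draw, and choose one of two designs before forms are printed:

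- use the same questions in every round; or
- draw separately for each respondent, or rotate balanced forms within each hospital and round, so that all 18 questions appear at every time point.

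The first is simplest, but doctors meet the same questions three times. The second keeps the whole bank in use.

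Under either design, record which questions each doctor received, and fix in advance a right/wrong rule for items with several correct options. Analyse item-level answers with a logistic mixed model: question and condition as fixed effects, and random effects for hospital and for respondent within survey. The respondent effect is needed because one doctor's 8 answers are correlated. With an assumed correlation of 0.05 to 0.20, the variance inflation is 1 + 7 × 0.05 = 1.35 to 1 + 7 × 0.20 = 2.40, and a nominal 5% test that ignores it runs at about 9% to 21%.

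The cost is several printed versions (for the second design), item-level data entry and a slightly longer model. The question bank, the 8 questions per doctor and the 10-minute limit stay as they are.
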